10.1.2 Consent for minors when they reach the age of majority

N/A

10.1.3 Participation of Subjects who are/become Impaired in Decision Making

For participants addressed in section 5.4, an LAR will be identified consistent with Policy 403 and informed consent obtained from the LAR, per section 10.1.

10.2 STUDY DISCONTINUATION AND CLOSURE

This study may be temporarily suspended or prematurely terminated if there is sufficient reasonable cause. Written notification, documenting the reason for study suspension or termination, will be provided

Abbreviated Title: Fostamatinib for post-transplant cytopenias

Version Date: 11/28/2023

by the suspending or terminating party to study participants, investigator, the Investigational New Drug (IND) sponsor and regulatory authorities. If the study is prematurely terminated or suspended, the Principal Investigator (PI) will promptly inform study participants, the Institutional Review Board (IRB), and sponsor and will provide the reason(s) for the termination or suspension. Study participants will be contacted, as applicable, and be informed of changes to study visit schedule.

Circumstances that may warrant termination or suspension include, but are not limited to:

- Determination of unexpected, significant, or unacceptable risk to participants
- Demonstration of efficacy that would warrant stopping
- Insufficient compliance to protocol requirements
- Data that are not sufficiently complete and/or evaluable
- Determination that the primary endpoint has been met

Study may resume once concerns about safety, protocol compliance, and data quality are addressed, and satisfy the sponsor, IRB and/or Food and Drug Administration (FDA).

10.3 CONFIDENTIALITY AND PRIVACY

Participant confidentiality and privacy is strictly held in trust by the participating investigators, their staff, and the sponsor(s) and their interventions. This confidentiality is extended to cover testing of biological samples and genetic tests in addition to the clinical information relating to participants. Therefore, the study protocol, documentation, data, and all other information generated will be held in strict confidence. No information concerning the study or the data will be released to any unauthorized third party without prior written approval of the sponsor.

All research activities will be conducted in as private a setting as possible.

The study monitor, other authorized representatives of the sponsor, representatives of the Institutional Review Board (IRB), and/or regulatory agencies may inspect all documents and records required to be maintained by the investigator, including but not limited to, medical records (office, clinic, or hospital) and pharmacy records for the participants in this study. The clinical study site will permit access to such records.

The study participant's contact information will be securely stored at each clinical site for internal use during the study. At the end of the study, all records will continue to be kept in a secure location for as long a period as dictated by the reviewing IRB, Institutional policies, or sponsor requirements.

Study participant research data, which is for purposes of statistical analysis and scientific reporting, will be transmitted to and stored at the NHLBI OCD. This will not include the participant's contact or identifying information. Rather, individual participants and their research data will be identified by a unique study identification number. The study data entry and study management systems used by clinical sites will be secured and password protected. At the end of the study, all study databases will be de-identified and archived at the NHLBI OCD.

To further protect the privacy of study participants, a Certificate of Confidentiality has been issued by the National Institutes of Health (NIH). This certificate protects identifiable research information from forced disclosure. It allows the investigator and others who have access to research records to refuse to disclose identifying information on research participation in any civil, criminal, administrative, legislative, or other proceeding, whether at the federal, state, or local level. By protecting researchers and institutions from being compelled to disclose information that would identify research participants, Certificates of Confidentiality help achieve the research objectives and promote participation in studies by helping assure confidentiality and privacy to participants.

Abbreviated Title: Fostamatinib for post-transplant cytopenias

Version Date: 11/28/2023

10.4 FUTURE USE OF STORED SPECIMENS AND DATA

We may share specimens and data with other researchers for future research to better understand post transplant cytopenia(s).

Following analyses of biospecimens for primary research purposes as described in the protocol, remaining samples suitable for future research will be stored in manner that conforms with DIR policy (such as BSI) or in a publicly accessible research biospecimen repository following IRB approval. Currently there is no plan to perform genetic testing on the samples. Collected samples will be de-identified prior to storage following current NHLBI DIR BSI Policy. An electronic database is used to store patient information related to the coded samples. Hard copy records or electronic copies of documents containing patient information are kept in the locked laboratory or other controlled access locations.

Coded biospecimens may be sent to collaborators outside of the NIH with IRB approval in accordance with applicable NIH and DIR Policy for sharing research resources, including an executed material transfer agreement (MTA). Biospecimens may be destroyed only when permitted by the clinical director and approved by the IRB. Any future research use of identifiable biospecimens not defined in the research protocol will occur only after IRB review and approval.

10.5 SAFETY OVERSIGHT

Safety oversight will be under the direction of a Data and Safety Monitoring Board (DSMB) composed of individuals with the appropriate expertise, including hematology and oncology Members of the DSMB should be independent from the study conduct and free of conflict of interest, or measures should be in place to minimize perceived conflict of interest. The DSMB will meet at least semiannually to assess safety and efficacy data on each arm of the study. The DSMB will operate under the rules of an approved charter that will be written and reviewed at the organizational meeting of the DSMB. At this time, each data element that the DSMB needs to assess will be clearly defined. The DSMB will provide its input to [name], who is the sponsor's authorized representative for the NHLBI Office of the Clinical Director

10.6 CLINICAL MONITORING

As per ICH-GCP 5.18 and FDA 21 CFR 312.5 clinical protocols are required to be adequately monitored by the study sponsor. The monitoring of this study will be conducted by Clinical Research Associates (CRAs)/Monitors employed by an independent contract organization working under an agreement with NHLBI to monitor aspects of the study in accordance with the appropriate regulations and the approved protocol. The objectives of a monitoring visit will be: 1) to verify the existence of signed informed consent form (ICF) and documentation of the ICF process for each monitored subject; 2) to verify the prompt and accurate recording of all monitored data points, and prompt reporting of all SAEs; UPs, and deviations, 3) to compare abstracted information with individual subjects' records and source documents (subject's charts, laboratory analyses and test results, physicians' progress notes, nurses' notes, and any other relevant original subject information); and 4) to help ensure investigators are in compliance with the protocol and with the appropriate regulations. The monitors also will inspect the clinical site regulatory files to ensure that regulatory requirements (Office for Human Research Protections-OHRP) and applicable guidelines (ICH-GCP) are being followed. During the monitoring visits, the investigator (and/or designee) and other study personnel will be available to discuss the study progress and monitoring visit.

The investigator (and/or designee) will make study documents (e.g., consent forms and pertinent hospital or clinical records) readily available for inspection by the local IRB, the site monitors, and the NHLBI staff for confirmation of the study data.

Abbreviated Title: Fostamatinib for post-transplant cytopenias

Version Date: 11/28/2023

10.7 QUALITY ASSURANCE AND QUALITY CONTROL

Each clinical site will perform internal quality management of study conduct, data and biological specimen collection, documentation and completion. An individualized quality management plan will be developed to describe a site's quality management.

Quality control (QC) procedures will be implemented beginning with the data entry system and data QC checks that will be run on the database will be generated. Any missing data or data anomalies will be communicated to the site(s) for clarification/resolution.

Following written Standard Operating Procedures (SOPs), the monitors will verify that the clinical trial is conducted and data are generated and biological specimens are collected, documented (recorded), and reported in compliance with the protocol, International Conference on Harmonisation Good Clinical Practice (ICH GCP), and applicable regulatory requirements (e.g., Good Laboratory Practices (GLP), Good Manufacturing Practices (GMP)).

The investigational site will provide direct access to all trial related sites, source data/documents, and reports for the purpose of monitoring and auditing by the sponsor, and inspection by local and regulatory authorities.

10.8 DATA HANDLING AND RECORD KEEPING

10.8.1 Data Collection and Management Responsibilities

Data collection is the responsibility of the clinical trial staff at the site under the supervision of the site investigator. The investigator is responsible for ensuring the accuracy, completeness, legibility, and timeliness of the data reported.

All source documents should be completed in a neat, legible manner to ensure accurate interpretation of data.

Hardcopies of the study visit worksheets will be provided for use as source document worksheets for recording data for each participant enrolled in the study. Data recorded in the electronic case report form (eCRF) derived from source documents should be consistent with the data recorded on the source documents.

Clinical data (including inpatient concomitant medications and clinical laboratory data) will either be entered into CTDB, a 21 CFR Part 11-compliant data capture system, and/or will be imported on Excel file(s) from the site's electronic health records system. Adverse events (AEs) grade 3 and above will be entered into CTDB.

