2.3 RISK/BENEFIT ASSESSMENT

2.3.1 Known Potential Risks

Fostamatinib

Abbreviated Title: Fostamatinib for post-transplant cytopenias

Version Date: 11/28/2023

Fostamatinib is currently FDA approved for the treatment of refractory chronic ITP. To date, over 4,000 patients have received fostamatinib as part of randomized controlled and open label trials across a variety of disease states including rheumatoid arthritis, ITP, autoimmune hemolytic anemia, and oncologic diseases. It has a consistent safety profile and the most common adverse reactions ($\geq 5\%$ and more than placebo) are diarrhea, hypertension, nausea, respiratory infection, dizziness, ALT/AST increased, rash, abdominal pain, fatigue, chest pain and neutropenia. Warnings and precautions included in the US product label include hypertension, elevated liver function tests, diarrhea, neutropenia, and embryo-fetal toxicity.

Hypertension	Hypertensive crisis occurred in 1% of patients and patients with pre-existing hypertension may be more susceptible
Hepatotoxicity	AST/ALT levels more than 3x the upper limit of normal occurs in 9% of patients
Diarrhea	Occurred in 31% of patients treated but with only 1% of patients developing severe diarrhea
Neutropenia	Occurred in 6% of patients with febrile neutropenia occurring in 1%
Embyro-fetal toxicity	Based on findings from animal studies and mechanism of action fostamatinib can cause fetal harm.

Concomitant use of strong CYP3A4 inhibitors with fostamatinib will increase exposure to R406 that may result in increased risk of adverse reactions while concomitant use of strong CYP3A4 inducers reduces exposure to R406. Fostamatinib may increase the concentration of some CYP3A4 substrate drugs, some BCRP substrate drugs (ex. rosuvastatin), and some P-glycoprotein substrate drugs (e.g. Digoxin). Especially in transplant subjects, there is the concern for drug-drug interactions with strong CYP3A4 inhibitors, particularly frequently used anti-fungal medications including voriconazole, posaconazole, ketoconazole and itraconazole. If a subject is on a strong CYP3A4 inhibitor and is unable to be switched to a moderate or low CYP3A4 inhibitor, the starting dose of fostamatinib for the 1st 4 weeks would be 150 mg daily which can be escalated to 100 mg BID if refractory cytopenias persist AND the patient appears able to tolerate the higher dose of treatment as determined on the 4-week assessment visit.

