- In the event that the subject is unable to tolerate 100 mg BID, the dose can be reduced to 150mg daily with re-assessment. If intolerable AEs with 150 mg daily, dose can be reduced to 100 mg daily. If unable to tolerate 100mg daily, patient will stop fostamatinib and will be off study. Intolerance is considered as any grade 3-4 AEs, probably or definitely related to fostamatinib, or any grade AE which, at the PI's discretion, appears to be distressing enough to the patient to lead to the drug's discontinuation. If the adverse events resolved and subject tolerates the dose reduction with no recurrence of AE, per PI discretion subject can be re-escalated one level at a time until back to the maximum tolerable dose.
- Causes of neutropenia in a AHCT recipient may include: infections such as cytomegalovirus infection, medication such as ganciclovir or other antibiotics, immunosuppressants such as mycophenolate or ruxolitinib, graft failure, relapse of primary disease. If neutropenia occurs, we will perform an extensively work up on the patient for the other causes stated above, and/or hold other potential culprit medications. We will give filgrastim to patients while doing the above work up. If no other causes are found, and the neutropenia does not recover, or recurs, with holding other medications, we will conclude that fostamatinib is contributing to the development of neutropenia.
- GvHD may mimic adverse events. If holding fostamatinib according to the DSR does not reverse the diarrhea, abdominal pain, transaminase elevation, AND there are no other causes (such as infection) identified, we will consider the cause of the adverse events to possibly be related to GVHD. In such circumstances, we will make every effort possible to perform biopsies of the involved organ systems to confirm the diagnosis of GvHD.

Dose adjustment for platelet counts and hemoglobin are as the following:

Thrombocytosis	
PLT $\geq 200 \times 10^9 /L$ to $\leq 400 \times 10^9 /L$ at any time	
 • Decrease the dose to the next lower dose level. Wait 2 weeks to assess the effects of this and any subsequent dose adjustments.
PLT $> 400 \times 10^9 /L$ at any time	
 • Stop fostamatinib. Increase the frequency of platelet monitoring to twice weekly. • Once the platelet count is $< 150 \times 10^9 /L$, resume fostamatinib at the next lower dose level

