7 STUDY INTERVENTION DISCONTINUATION AND PARTICIPANT DISCONTINUATION/WITHDRAWAL

7.1 DISCONTINUATION OF STUDY INTERVENTION

See section 6.1.2.3 for information on dosing modifications or discontinuation rules based on laboratory abnormalities or other adverse events.

Abbreviated Title: Fostamatinib for post-transplant cytopenias

Version Date: 11/28/2023

Subjects who have the study product stopped for safety related issues will not continue with dosing. In addition, subjects who have an allergic reaction that is temporally associated with study product administration and the PI believes it to be related to study product will not receive any more study product.

In addition, a subject in this clinical study may discontinue study drug at their request for any reason. Every effort should be made to encourage subjects to remain in the study for the duration of their planned outcome assessments. Subjects should be educated on the continued scientific importance of their data, even if they discontinue study drug.

Discontinuation from the study drug does not mean discontinuation from the study, and remaining study procedures should be completed as indicated by the study protocol. If a clinically significant finding is identified (including, but not limited to changes from baseline) after enrollment, the investigator or qualified designee will determine if any change in participant management is needed. Any new clinically relevant finding will be recorded as an adverse event (AE).

The data to be collected at the time of study intervention discontinuation will include the following:

- Reason for discontinuation
- Any adverse event
- Patients will be followed for clinical data required for the duration of the study

Participants are free to withdraw from participation in the study at any time upon request.

An investigator may discontinue or withdraw a participant from the study for the following reasons:

- Disease progression which requires discontinuation of the study intervention
- If any clinical adverse event (AE), laboratory abnormality, or other medical condition or situation occurs such that continued participation in the study would not be in the best interest of the participant
- Investigator discretion
- Positive pregnancy test
- Participant unable to receive study drug
- Participant non-compliance, defined as missing >20% of the study drug during any 4-week study interval

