8.4.3 Classification of an Adverse Event

8.4.3.1 Severity of Event

This study will utilize the Common Terminology Criteria for Adverse Events version 5.0 (CTCAE v5.0) for toxicity and adverse event reporting. A copy of the CTCAE v5.0 can be downloaded from the https://ctep.cancer.gov/protocolDevelopment/electronic_applications/ctc.htm.

AEs will be recorded, verified, and followed until satisfactory resolution or stabilization.

Severity definitions found in the CTCAE v5.0 will be used for grading the severity (intensity) of AEs:

- 1) **Mild (Grade 1):** Asymptomatic or mild symptoms; clinical or diagnostic observations only; intervention not indicated.
- 2) **Moderate (Grade 2):** Minimal, local or noninvasive intervention indicated; limiting age-appropriate instrumental ADL*
- 3) **Severe (Grade 3):** Severe or medically significant but not immediately life-threatening; hospitalization or prolongation of hospitalization indicated; disabling; limiting self-care ADL**.
- 4) **Life-threatening (Grade 4):** Life-threatening consequences; urgent intervention indicated.
- 5) **Death (Grade 5):** Death related to AE.

*Instrumental ADL refer to preparing meals, shopping for groceries or clothes, using the telephone, managing money, etc.

**Self-care ADL refer to bathing, dressing and undressing, feeding self, using the toilet, taking medications, and not bedridden.

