8.4.4 Time Period and Frequency for Event Assessment and Follow-Up

The occurrence of an adverse event (AE) or serious adverse event (SAE) may come to the attention of study personnel during study visits and interviews of a study participant presenting for medical care, or upon review by a study monitor.

Grade 3 and 4 AE, clinically significant laboratory abnormalities, and all SAEs occurring from the initiation of the study drug through the last visit will be will be captured on the appropriate case report form (CRF). All grade 3-4 AEs and all SAEs will be followed to adequate resolution, or until the investigator deems the event to be chronic or the participant is stable.

Any medical condition that is present at the time that the participant is screened will be considered as baseline and not reported as an AE. However, if the study participant's condition deteriorates and that event reaches grade 3 and above, or becomes an SAE at any time after the first dose of the study drug, it will be recorded as an AE. For the purposes of baseline documentation, a medical condition is described as a group of signs and symptoms clearly related to a disease, illness or injury; any physiologic, mental or psychological condition or disorder and will be captured as a single event.

Changes in the severity of an AE will be documented to allow an assessment of the duration of the event at each level of severity to be performed. AEs characterized as intermittent require documentation of onset and duration of each episode.

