8.4.5 Adverse Event Recording

Information on grade 3 and 4 AEs, clinically significant laboratory abnormalities, and all SAEs, occurring from the initiation of the study drug through the last visit will be recorded on the appropriate CRF. All clearly related signs, symptoms, and results of diagnostic procedures performed because of an AE should be grouped together and recorded as a single diagnosis. If the AE is a laboratory abnormality that is part of a clinical condition or syndrome, it should be recorded as the syndrome or diagnosis rather than the individual laboratory abnormality. Each AE will also be described in terms of duration (start and stop date), severity, association with the study product, action(s) taken, and outcome. Clinician's assessment of severity, relationship to study product should be assessed only by those with the training and authority to make a diagnosis.

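### The AE recording rules conflict, so a non-serious symptomatic grade 1–2 AE that changes the dose need not reach the CRF, and one that stops the drug needs no causality grade

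*Combined protocol and SAP*

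**What the plan says.** The combined protocol and SAP gives three different scopes for recording AEs.

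- **No grade limit.** Section 8.4.3.1 says "AEs will be recorded, verified, and followed until satisfactory resolution or stabilization". Section 7.1 likewise has any new finding of clinical relevance after enrollment recorded as an AE. It also lists what is collected when study drug is stopped, including the reason and any adverse event.
- **Grade 3–4, laboratory, SAE.** Section 8.4.4 puts on the CRF "Grade 3 and 4 AE, clinically significant laboratory abnormalities, and all SAEs occurring from the initiation of the study drug through the last visit". Section 8.4.5 repeats the same three categories. The causality assessment in 8.4.3.2 is required only for these categories.
- **Grade 3 and above.** Section 10.8.1, on the database, says "Adverse events (AEs) grade 3 and above will be entered into CTDB".

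Three other sections use AEs below grade 3. Section 6.1.2.3 counts as intolerance not only related grade 3–4 events but also "any grade AE which, at the PI's discretion, appears to be distressing enough to the patient to lead to the drug's discontinuation", and intolerance moves the subject down the dose steps or off drug. Section 8.4.7 names diarrhea among the items to be followed closely, without a grade. Section 9.1 treats a stop before week 4 differently according to whether it was related to treatment.

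**The concern.** A site cannot tell from the text whether a grade 2 symptom should be recorded. If it follows 8.4.4, 8.4.5 and 10.8.1, the trial can hold a dose reduction with no AE behind it in the data.

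Two uses of the data are at stake. The first is the descriptive AE summary planned in 9.3.1, which would understate symptomatic tolerability in a post-transplant population taking many other drugs. The second is the response classification in 9.1 and 9.2.1, which turns on relatedness. That judgement is not required for a low-grade AE, even one that ends treatment.

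**Working it through.** The plan states no figure on this point to reproduce, so the check has three parts: what each rule captures, the size for the one symptom with usable rates, and the route to the primary endpoint.

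**1. What the rules require, by type of event**

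| Event | CRF or database entry required? | Causality required (8.4.3.2)? |
|---|---|---|
| SAE, any grade | Yes (8.4.4, 8.4.5) | Yes |
| Clinically significant laboratory abnormality, any grade | Yes (8.4.4, 8.4.5); laboratory data also enter the database (10.8.1) | Yes |
| Blood pressure | Measured at every follow-up visit (8.3) | Not by itself |
| Grade 3–4 AE | Yes | Yes |
| Non-serious symptomatic grade 1–2 AE leading to discontinuation | Collected under 7.1; outside the limits in 8.4.4, 8.4.5 and 10.8.1 | No |
| Non-serious symptomatic grade 1–2 AE leading to reduction or interruption | Not under 8.4.4, 8.4.5 or 10.8.1 | No |
| Other non-serious symptomatic grade 1–2 AE, including diarrhea | Not under 8.4.4, 8.4.5 or 10.8.1 | No |

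The sixth row is not hypothetical. Besides the intolerance clause, the hepatotoxicity table in 6.1.2.3 makes symptoms such as nausea or abdominal pain decide whether drug is interrupted when AST/ALT has tripled from enrollment but is still below 3 x ULN. The laboratory value reaches the database; the symptom need not.

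**2. Size for diarrhea**

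Inputs: 31% any diarrhea, "with only 1% of patients developing severe diarrhea" (2.3.1); 20 evaluable subjects and up to 8 more (9.1). Section 8.4.3.1 labels grade 3 as severe, so severe is read as grade 3 or above.

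- Share below the grade 3 rule: (31 − 1)/31 = 30/31 = 97%.
- n = 20: expected cases 0.31 × 20 = 6.2; meeting the rule 0.01 × 20 = 0.2. Chance that at least one case meets the rule: 1 − 0.99^20 = 18%.
- n = 28: 0.31 × 28 = 8.7; 0.01 × 28 = 0.28; 1 − 0.99^28 = 25%. This is an upper case, because the 8 additional enrollments allow for subjects who leave treatment before week 4.

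**3. Route to the primary endpoint**

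Under 9.1, a stop due to a drug-related AE counts as non-response and is not replaced. A stop before week 4 for reasons unrelated to treatment or progression is not evaluated, and additional subjects may be enrolled. The grade 3–4 part of the intolerance definition requires probable or definite relatedness; the any-grade part does not. So a low-grade AE can end treatment before week 4 without the judgement that 9.1 needs.

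Rejection of the null requires more than 4 responses in 20. Take 4 responders among 20, one of the other 16 being such a stop: the null is not rejected. If that stop is instead not evaluable and the replacement responds, the count is 5 of 20 and the null is rejected. The replacement responds with probability 0.10 under the null rate and 0.35 under the alternative. How often such stops occur cannot be computed from the documents.

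**4. What does not change**

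The TRSAE rule in 9.3.4 counts treatment-related SAEs. All SAEs are captured with causality. Recomputing the boundary from the beta(1, 3) prior and the 90% posterior threshold returns the printed table, and AE grade does not enter it.

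**The case against.** The strongest case on the other side is that selective capture is a legitimate choice. Fostamatinib is approved, over 4,000 patients have received it (2.3.1), the trial is a small efficacy study, and safety stopping rests on SAEs. AEs are assessed at each follow-up visit (8.3), so source notes may hold low-grade events. The any-grade clause speaks of events leading to discontinuation, and 7.1 already collects the reason and any AE at that moment. Most of the 97% would be diarrhea handled by supportive measures, which changes no dose.

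Much of this stands, and it limits the point. A reader might infer three stronger things that the documents do not support:

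- **That only grade 3+ AEs are recorded and most tolerability events will be lost.** SAEs and clinically significant laboratory abnormalities are captured at any grade. The 97% is for diarrhea alone; no grade split is given for nausea, rash, fatigue, dizziness or abdominal pain.
- **That the items of special interest go mostly uncounted.** Nine of the ten in 8.4.7 are blood pressure or laboratory values, collected whatever the AE grade. Only diarrhea is exposed.
- **That the 14-day withdrawal rule runs on unrecorded events.** It covers neutropenia, LFT elevation and diarrhea. The first two are laboratory findings, and 6.1.2.3 interrupts drug for diarrhea only from grade 3.

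Three things survive: the conflict between sections, the uncaptured AE behind a dose change short of stopping, and the missing causality grade behind a stop.

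**Conclusion.** The concern holds in a narrow form, as an inexpensive improvement rather than a threat to the trial. The recording rules contradict one another. Read as written, they leave out non-serious symptomatic grade 1–2 AEs that reduce or interrupt the dose, and they require no causality assessment for those that end treatment. For diarrhea, the AE summary would be expected to show about 0.2 of 6.2 cases in 20 subjects.

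That size assumes that the 31% and 1% in 2.3.1, which describe previously treated patients, carry over to this population, and that severe means grade 3 or above. It counts only the grade 3 rule, so a lower-grade case that was serious or ended treatment would be an extra capture. The effect on response classification is real in logic, and one subject can decide a result at the boundary, but its frequency is unknown.

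**What to change.** Reconcile 7.1, 8.4.3.1, 8.4.4, 8.4.5 and 10.8.1 so that they state one recording scope. In 8.4.3.2, 8.4.4, 8.4.5 and 10.8.1, require CRF/CTDB entry, with grade and causality, of:

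1. any AE of any grade that leads to dose reduction, interruption or discontinuation of study drug;
2. diarrhea of any grade.

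Keep the current limit for all other AEs. Do not add any-grade AE entries for hemoglobin, platelets or other laboratory values. They are already in the database, and low hemoglobin and platelets are what subjects are enrolled for, so such entries would mostly restate the baseline disease that 8.4.4 excludes.

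The change concerns data capture only and leaves dosing rules as they are. The cost is a few extra CRF entries per subject for 20 to 28 subjects, whose AEs are already assessed at each visit.
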